1.2. INVESTIGATIONAL PRODUCT

1.2.1. Description

| Reference | Batch# | Form | Packaging | Confidentiality procedure | Storage temperature |
|---|---------|------------------|-----------|---------------------------|---------------------|
| Product ref: 16300.04 | 120918A | Yellowish liquid | Tube | Encoded | Room temperature |
| Placebo ref: 16300.06 Lot 120918B | 120918B | Yellowish liquid | Tube | Encoded | Room temperature |

1.2.2. Application

| | Zone | Frequency | Mode |
|--|------|--|------|
| Product ref : 16300.04 Lot 120918A | Body | 
 • Group A : 4 patients; Lithium liposome 1 application / day (evening) on target lesions on one side of the body, placebo 1 application / day (evening) on contralateral target lesions and excimer lamp on target lesions on the two sides; | |
| Placebo ref: 16300.06 Lot 120918B | Body | 
 • Group B : 4 patients; Liposomal Lithium 2 applications / day (morning and evening) on target lesions on one side of the body, placebo 2 applications / day (morning and evening) on contralateral target lesions and excimer lamp on target lesions on the two sides; • Groupe C : 4 patients; Lithium liposome 2 applications / day (morning and evening) on one side, placebo 2 applications / day (morning and evening) on contralateral target lesions. | |

1.2.3. Labelling

Example of labelling of each product by EUROFINS Dermascan and translation:

| DERMSCAN Etude n° | DERMSCAN Study # |
|--|------------------------------------|
| N° vol : | Subject#..... |
| Côté :..... | Side :..... |
| Posologie : | Posology : |
| En cas d'urgence : n° tél..... | In case of emergency : Tel # |
| Conservation : | Conservation : |
| A tenir hors de portée et de la vue des enfants. A utiliser sous stricte surveillance médicale pour essai clinique.médicale pour essai clinique. | |
| Keep out of reach and sight of children. To be used only under strict medical supervision for clinical trial. | |

1.2.4. Storage

Until the beginning of the study, products are kept at room temperature in a dedicated air-conditioned room, which is locked and access controlled.

1.2.5. Attribution to the subjects

➔ Products

Each product is attributed to volunteers according to the randomization in **Appendix 5.1**.

➔ Application zones

The application side (right/left) of the products (product/ placebo) are randomized according to the randomization list set previously.

1.2.6. Handing-out

The products are delivered to the subjects by the investigator with an explanation of the application mode and frequency.

1.2.7. Future

As far as possible, one sample of the study products is kept by the investigation center for a period of six months after its receipt.

- By default, the products (used and not used) are destroyed at the end of the study according to the current internal EUROFINS Dermascan/Pharmascan procedures.

1.3. STUDY STAGES

BEFORE THE BEGINNING OF THE STUDY

Technician:

- weighs the study products before their use.

Twice a week:

Patients of both groups A and B come to the hospital where the lesions will be exposed with a Quantel 308 excimer lamp that delivers a narrow UVB spectrum centered of a wavelength of around 308nm. This lamp makes it possible to perform phototherapy localized on the target lesion. Fluences will be performed twice a week throughout the duration of the study.

ON D0**Patients:**

- come to the investigation center without having applied any product to the body since the previous evening;
- are informed about the trial objectives, the procedures and the risks of the study with the information sheet;
- sign two copies of the Consent Form.

Dermatologist:

- verifies inclusion and non-inclusion criteria;
- performs a standardized photo of each target lesion;
- traces and identifies the perimeter of each target lesion (1 to 3 on each side) on a tracing sheet (the natural marks such the scars, moles, tattoos or others will be also reported on the tracing sheet in order to easily find the target lesions);
- performs a clinical examination of the skin on the application area;
- asks the subjects about their usual unpleasant sensations;
- explains to the subjects the product application conditions and frequency;
- gives to the subjects:
 - the product to be used according to the instructions in 2.1.2 and 2.2.2,
 - the daily log to write down their possible unpleasant sensations or medications,

ON M1 (last application being done the previous day)**Subjects:**

- return to the hospital with no product applied to the body since the previous evening;
- bring back their daily log;

Dermatologist:

- performs a standardized photo of each target lesion;
- traces and identifies the perimeter of each target lesion (1 to 3 on each side) on a tracing sheet (the natural marks such the scars, moles, tattoos or others will be also reported on the tracing sheet in order to easily find the target lesions);
- performs a clinical examination of the skin on the application area;
- asks the subjects about the unpleasant sensations they felt during the study and assesses the cutaneous acceptability of the study product;
- collection of the concomitant treatments and undesirable effects.

On M2 (the last application being done the previous night):**Subjects:**

- return to the hospital with no product applied to the body since the previous evening;
- bring back their daily log;

Dermatologist:

- performs a standardized photo of each target lesion;
- traces and identifies the perimeter of each target lesion (1 to 3 on each side) on a tracing sheet (the natural marks such the scars, moles, tattoos or others will be also reported on the tracing sheet in order to easily find the target lesions);
- performs a clinical examination of the skin on the application area;
- asks the subjects about the unpleasant sensations they felt during the study and assesses the cutaneous acceptability of the study product;
- collection of the concomitant treatments and undesirable effects.

On M3 (the last application being done the previous night):**Subjects:**

- return to the hospital with no product applied to the body since the previous evening;
- bring back their daily log and the products;
- stop the treatment.

Dermatologist:

- performs a standardized photo of each target lesion;
- traces and identifies the perimeter of each target lesion (1 to 3 on each side) on a tracing sheet (the natural marks such the scars, moles, tattoos or others will be also reported on the tracing sheet in order to easily find the target lesions);
- performs a clinical examination of the skin on the application area;
- asks the subjects about the unpleasant sensations they felt during the study and assesses the cutaneous acceptability of the study product;
- collection of the concomitant treatments and undesirable effects.

On M4 (one month after the last product application):**Subjects:**

- return to the hospital with no product applied to the body since the previous evening;
- bring back their daily log and the products;
- performs clinical scores on an analog visual scale.

Dermatologist:

- performs a standardized photo of each target lesion;
- traces and identifies the perimeter of each target lesion (1 to 3 on each side) on a tracing sheet (the natural marks such the scars, moles, tattoos or others will be also reported on the tracing sheet in order to easily find the target lesions);
- performs a clinical examination of the skin on the application area;
- asks the subjects about the unpleasant sensations they felt during the study and assesses the cutaneous acceptability of the study product;
- collection of the concomitant treatments and undesirable effects.

AT THE END OF THE STUDY**Technician:**

- weighs the study products after their use.

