| Objectives | 
Primary objective:
 
 • Evaluate the percentage of repigmentation observed one month after the end of three months of treatment measured on an objective layer by image analysis; 
Secondary objectives: Evaluate:
 
 • the percentage of repigmentation observed after one, two and three months of treatment measured on an objective layer by image analysis; • the ability of the product to maintain the human body in good condition (cutaneous acceptability) by clinical examination by the dermatologist; • Patient satisfaction using a visual analogue scale from 0 to 10. • The illustrative effect using standardized photographs; • The quantity of product by weighing the tubes. • The occurrence of possible adverse effects. | | | | | | | | | | | | | | | | | | | | | | | | | | | | | | | | | | | | | | | | | | | | | | | | | | | | | | | | | | | | | | | | | | | | | | | | | | | | | | | | | | | | |
|---|--|---------|-----------------|---------|---------|-------|----|----|-------------------|---|---|---|---|---|---|---|---|---|---|---|---|---|--|---|---|---|---|---|---|--|---|---|---|---|---|---|---|---|---|---|---|---|---|---|---|---|---|---|---|---|---|---|---|---|---|---|---|---|---|---|---|---|---|---|-------------------------------|---|---|---|---|---|---|--|----------|---------|---------|---------|---------|-------|--|----------|---|---|---|---|-------|
| | 
 • Study in proof of concept; • Double blind study; • Comparative study, versus placebo in intra-individual; • Three parallel groups testing different dosages / combinations of treatments; • Randomized. | | | | | | | | | | | | | | | | | | | | | | | | | | | | | | | | | | | | | | | | | | | | | | | | | | | | | | | | | | | | | | | | | | | | | | | | | | | | | | | | | | | | |
| Methodology | | | | | | | | | | | | | | | | | | | | | | | | | | | | | | | | | | | | | | | | | | | | | | | | | | | | | | | | | | | | | | | | | | | | | | | | | | | | | | | | | | | | | |

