2.3. LESIONS EXPOSURE TO EXCIMER LAMP

The lesions will be exposed to a Quantel 308 excimer lamp that delivers a narrow UVB spectrum centered around the 308nm wavelength. This lamp makes enables to carry out phototherapy localized on the target lesion. The fluences will be performed twice a week during the whole study according to the recommendations of the French Society of Dermatology regarding phototherapy. The initial dose of 50 mJ / cm² will be increased then progressively every 2 sessions until getting a franc erythema lasting less than 48h and not causing phlyctenes.

excimer lamp Quantel 308

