5. APPENDICES – STUDY DOCUMENTS

5.1. RANDOMIZATION LIST (GROUPS ATTRIBUTION)

RANDOMIZATION LIST
STUDY 18E1721
17/09/2019

| ID | Groupe | Côté Droit | Côté Gauche |
|----|--------|------------|-------------|
| 1 | A | Produit A | Produit B |
| 2 | B | Produit B | Produit A |
| 3 | C | Produit A | Produit B |
| 4 | A | Produit B | Produit A |
| 5 | A | Produit B | Produit A |
| 6 | B | Produit A | Produit B |
| 7 | B | Produit B | Produit A |
| 8 | A | Produit A | Produit B |
| 9 | C | Produit B | Produit A |
| 10 | C | Produit A | Produit B |
| 11 | C | Produit B | Produit A |
| 12 | B | Produit A | Produit B |

Groupe A: 1 application/ jour (le soir) + lampe

Groupe B: 2 applications/ jour (matin et soir) + lampe

Groupe C: 2 applications/ jour (matin et soir)

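### Is the primary M4 measurement in Groups A and B really taken after treatment has ended, when the excimer lamp runs for the whole study?

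*Combined protocol and SAP*

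**What the plan says.** The primary objective in the synopsis is to "Evaluate the percentage of repigmentation observed one month after the end of three months of treatment". The Methodology row describes "Three parallel groups testing different dosages / combinations of treatments".

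Section 1.2.2 gives Groups A and B product on one side, placebo on the other, and "excimer lamp on target lesions on the two sides". Group C has product and placebo without the lamp. The randomization list in section 5.1 matches this, for example "Groupe A: 1 application/ jour (le soir) + lampe".

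On duration, section 1.3 states for the lamp: "Fluences will be performed twice a week throughout the duration of the study". Section 2.3 repeats it: "The fluences will be performed twice a week during the whole study". At M3, section 1.3 has subjects return their log and products and then "stop the treatment". The next visit is headed "On M4 (one month after the last product application").

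Section 1.4 lists M4 against D0 among the efficacy comparisons. Section 1.4.1 defines the percentage change on each side and their difference. Section 1.4.2 limits the analysis to descriptive statistics.

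**The concern.** The primary objective reads as a measure of what persists once treatment is over. The study does not end at M3: M4 is a full visit with its own tracing, and the end-of-study tasks come after it. Taken literally, the lamp in Groups A and B therefore continues up to the primary measurement. If the lamp is part of the treatment, sections 1.3 and 2.3 conflict with the synopsis and with the stop at M3.

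At stake would be the meaning of the M4 result in two of the three groups: persistence after all therapy, or response under continuing phototherapy. The absolute repigmentation percentage, which is how the primary objective is worded, could differ between the two. So could any reading of Groups A and B beside Group C, which has no lamp.

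**Working it through.** **Patients concerned.** Section 5.1 assigns IDs 1, 4, 5 and 8 to Group A, IDs 2, 6, 7 and 12 to Group B, and IDs 3, 9, 10 and 11 to Group C. This reproduces the synopsis figure of 12 patients in groups of 4. Lamp groups: 4 + 4 = 8, and 8/12 = 67%.

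**Lamp exposure under each reading.** The frequency is two sessions a week (sections 1.3 and 2.3). The documents give no session count, so I assume a month of 28 to 30.4 days. Sessions = 2 × days / 7.

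| Interval | 28-day month | 30.4-day month |
|---|---|---|
| D0 to M3 | 3 × 8.0 = 24 | 3 × 8.69 = 26.1 |
| M3 to M4 | 2 × 28/7 = 8.0 | 2 × 30.4/7 = 8.69 |
| D0 to M4 | 4 × 8.0 = 32 | 4 × 8.69 = 34.7 |

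If the lamp stops at M3, the M3 to M4 row is 0. If it runs to M4, sessions before the primary measurement rise by 8/24 = 33%. That ratio is simply four months against three; it does not measure any effect on repigmentation, which the documents do not allow to be estimated.

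**What stops at M3.** The texts on each side are as follows.

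- *Topical product only.* The stop is in the list of things subjects do, directly after they hand back the products, at a visit whose heading refers to the last application. The lamp is given at the hospital, not by the patient. M4 is dated from the last product application, which fits the synopsis timing. Section 1.1.3 weighs products at D0 and after use at M3, and section 2.4 names M1, M2 and M3 as the visits after product use. The three months are thus a product-use period.
- *Product and lamp.* The Methodology row speaks of combinations of treatments, and Groups B and C differ only in the lamp, so the word there must include it. The non-inclusion criteria in section 1.1.1 also describe phototherapy as something one is treated with. Neither text concerns what ends at M3.

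The first reading has the direct evidence on timing and leaves every lamp statement intact. Under it the texts are compatible.

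**Effect on the product comparison.** Section 1.4.1 takes the product-side percentage change minus the placebo-side change within a patient. Suppose the lamp adds a common amount L to both sides. Then (P + L) − (Q + L) = P − Q, whether L reflects 24 sessions or 32. If the lamp's effect is not additive, the difference still compares product with placebo under the same lamp schedule. The side is randomized and even: in each group the list puts Produit A on the right in 2 patients and on the left in 2.

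**Effect on the absolute percentages.** In Groups A and B these include a lamp contribution on either reading, from 24 to 26 sessions or from 32 to 35. Neither version isolates the product.

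**The case for a change.** The strongest case for a change is that the synopsis, which holds the primary objective, itself uses *treatments* in a sense that includes the lamp. A reader of the objective alone would not learn that phototherapy continues in the final month. The balance between sides protects the difference but not the separate side percentages. The protocol also treats recent phototherapy as relevant, since it excludes patients who had it in the 4 weeks before randomization, about the length of M3 to M4. Finally, one member of staff might stop the lamp at M3 and another continue; in a group of 4, one patient handled differently is 25% of the group.

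Part of this stands. The text available for this review, which lacks a few pages, neither defines *treatment* nor states a last lamp session in so many words. The absolute M4 values in Groups A and B, and their reading beside Group C, depend on the answer.

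The rest has less force. Both lamp statements agree that it runs for the whole study, so anyone following the plan as written has one instruction on lamp duration. A patient whose lamp stopped early would still have the same exposure on both sides, so the within-patient difference would remain fair. A comparison of Group B with Group C carries at least three months of lamp in any case, rests on 4 patients per group, and is not tested.

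**Conclusion.** The concern does not call for a change to the plan. It identifies an undefined term, not a demonstrated contradiction. On the better-supported reading, M4 in Groups A and B (8 of 12 patients) is one month off product with the lamp continuing on both sides, and the synopsis and sections 1.3 and 2.3 agree. The product-minus-placebo difference is balanced on either reading. The 8 to 9 sessions at issue change only how the absolute M4 percentages in Groups A and B are described, and an analyst can state this in a table label or footnote without altering any calculation.

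This rests on three assumptions: both sides receive the same lamp schedule, as section 1.2.2 provides; a month is 28 to 30.4 days; and the unavailable pages do not define *treatment* otherwise. It is a reading of the text, with no view on when the lamp should stop. If the sponsor intends the M3 stop to include the lamp, the synopsis and sections 1.3 and 2.3 must be reconciled, and that choice is the sponsor's.

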1.4. DATA ANALYSIS

The following data are analyzed:

| | Parameter(s) | Unit(s) | Variation(s) DX/D0 Kinetics | Statistical analysis (tick if yes) | Expected result(s) |
|--------------------------------|---|-----------------|-----------------------------------|--|--------------------|
| Cutaneous acceptability | Clinical signs observed Functional and physical signs reported | / | D28/D0 | / | No worsening |
| Efficacy | Lesions surface | cm ² | M4/D0 M3/D0 M2/D0 M1/D0 | / | Decrease |
| Subjective evaluation | Analog visual scale from 0 to 10 | Score | / | / | / |

Individual data are presented in raw value tables. These tables also show the descriptive statistics: means, medians, minima, maxima, standard errors of the means (SEM) and confidence intervals of 95% (95% CI).

Variation tables present raw variations, percentage variations and descriptive statistics.

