1.4.1. Calculation formulas

| Product | Placebo |
|--|--|
| $\Delta Pdt = (Pdt_{ti} - Pdt_{t0})$ | $\Delta Pla = (Pla_{ti} - Pla_{t0})$ |
| $\Delta\% Pdt = \frac{(Pdt_{ti} - Pdt_{t0})}{Pdt_{t0}} \times 100$ | $\Delta\% Pla = \frac{(Pla_{ti} - Pla_{t0})}{Pla_{t0}} \times 100$ |
| $\Delta\Delta = \Delta Pdt - \Delta Pla$ | |
| $\Delta\Delta\% = \Delta\% Pdt - \Delta\% Pla$ | |

with:
 Pdt: value obtained on the zone treated by the tested product
 Pla: value obtained on the zone treated by the placebo
 t0: before product application
 ti: at each measurement time after product application

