2.2. ANALYSIS OF THE LESIONS SURFACE

2.2.1. Principle

On each visit, the perimeter of each target lesion and any possible repigmentation ranges inside it will be traced and identified on a tracing sheet. Natural marks such as scars, moles, tattoos or others will also be reported on the tracing sheet in a manner to find the target lesions easily.

An entire body drawing, front view and back view, must be present in the data collection notebook so that the lesions can be represented and numbered. The number of each lesion must also appear on the tracing sheet.

The surface measurement of each lesion (in cm²) will be made by the Sponsor, by image analysis of the tracing sheet under a video camera using a classical image analysis software.

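### The primary objective is percentage of repigmentation, but the only planned efficacy quantity is change in lesion surface, which is not fully defined and cannot separate repigmentation from outward spread

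*Combined protocol and SAP*

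**What the plan says.** The primary objective in the synopsis is "Evaluate the percentage of repigmentation observed one month after the end of three months of treatment measured on an objective layer by image analysis". No formula for a percentage of repigmentation appears in the document.

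In the table of section 1.4 the only efficacy parameter is lesion surface in cm². Its row reads "M4/D0 M3/D0 M2/D0 M1/D0 | / | Decrease": four comparisons with D0, and a decrease as the expected result. Section 1.4.1 gives, for each side, the raw and percentage change from D0, and then the product value minus the placebo value.

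On measurement, the rule in section 2.2.1 for every visit is that "the perimeter of each target lesion and any possible repigmentation ranges inside it will be traced and identified on a tracing sheet". The same sheet also carries natural marks so that the lesion can be found again. It then states: "The surface measurement of each lesion (in cm²) will be made by the Sponsor, by image analysis of the tracing sheet". It does not say which surface this is: the area within the outer perimeter, or that area less the inner repigmented areas. Neither section makes the D0 outline the reference for later visits.

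Three further provisions bear on the point:

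- Section 1.1.1 admits only stable lesions. The definition uses a 3-month criterion, no hypochromic margins in Wood's light and no confetti depigmentation.
- Section 1.4 tabulates individual raw values and variations.
- Section 1.4.2 limits the analysis to descriptive statistics.

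**The concern.** The area of a lesion retraced as it stands at each visit falls when skin repigments and rises when the border moves outward. A change in that area reflects both, and the plan never separates them. Two consequences follow.

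- Repigmentation can be masked on a side where the same lesion also extends.
- A favourable product-minus-placebo contrast can arise from less spread on the product side with no extra repigmentation.

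The handling of inner areas is a second gap in the same variable. If the measured surface is everything inside the outer perimeter, islands of repigmentation are traced but never counted.

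This is a placebo-controlled proof of concept with 4 patients per group and no inferential analysis, so the point estimates are the whole result. Repigmentation and slowed extension would be different conclusions about the product, and only the first answers the stated objective.

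**Working it through.** The plan gives no power, effect size or spread rate, so there is no figure of its own to reproduce. The check applies the formulas of section 1.4.1 to assumed values.

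**Notation.** A0 is the lesion area at D0, R the area repigmented inside the D0 outline, and S the new depigmented area outside it. R and S are assumed because the documents give neither.

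**Reading 1: inner repigmented areas are subtracted.** Area at a later visit is A0 - R + S, so

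Δ% = 100 × (S - R) / A0.

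Spread offsets repigmentation one for one. With R = 30% of A0:

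| Spread S (% of A0) | Δ% |
|---|---|
| 0 | -30 |
| 5 | -25 |
| 10 | -20 |
| 20 | -10 |
| 30 | 0 |

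**The contrast.** ΔΔ% is Δ% on product minus Δ% on placebo. Each pair below is product, then placebo, in % of A0.

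| Case | Repigmentation | Spread | Δ% | ΔΔ% | True difference in repigmentation |
|---|---|---|---|---|---|
| a | 0, 0 | 5, 20 | +5, +20 | -15 | 0 |
| b | 30, 30 | 10, 25 | -20, -5 | -15 | 0 |
| c | 40, 20 | 20, 0 | -20, -20 | 0 | 20 |
| d | 40, 20 | 0, 0 | -40, -20 | -20 | 20 |
| e | 15, 0 | 0, 0 | -15, 0 | -15 | 15 |

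Cases a, b and e give the same contrast, but only e contains a repigmentation benefit. In case c a 20-point benefit disappears. In case d, without spread, the two measures agree apart from sign.

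Cases b and c matter most. In both, each side shows the expected decrease, so the tabulated surfaces give no sign of a problem. In a group of 4, one patient like case b moves the mean ΔΔ% by -15/4 = -3.75 points.

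**Reading 2: only the outer perimeter is measured.** Inner repigmentation then drops out of R. A lesion that repigments 30% entirely as inner islands, without spread, reads as Δ% = 0. Outward spread is still counted in full.

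**Error in the component measures.** Separating R from S requires laying each tracing over the D0 tracing. For an unchanged circular lesion of radius r, a shift of d (small against r) creates false repigmentation of about 2d/(πr) of its area, and the same amount of false spread. Take an assumed d = 0.2 cm:

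- 10 cm²: r = √(10/π) = 1.78 cm, and 0.4/(π × 1.78) ≈ 7%.
- 2 cm² (the minimum surface in section 1.1.1): r = √(2/π) = 0.80 cm, and 0.4/(π × 0.80) ≈ 16%.

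The two false areas are equal, so they cancel in the net change but not in either component.

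**The case against.** The strongest reply has four parts.

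**Visibility in the tables.** A reader might infer that the plan will report slower spread on the product side as repigmentation. The documents do not support that. No section says a favourable ΔΔ% will be called repigmentation. Each side's change is computed and tabulated before the difference is taken, and the expected result is a decrease. In case a, both sides would be seen to grow. A placebo side at +20% beside a product side at 0% would be equally plain in a group of 4. This part stands, and it limits the point to the contrast and to masking within a side. It does not answer cases b and c.

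**Net change is not a documented definition.** A reader might also take the plan to define its endpoint as repigmented area minus newly depigmented area. It does not: section 2.2.1 leaves the measured surface open. This stands too, so the point is an undefined variable. Under either reading the variable departs from the objective.

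**Entry criteria.** The stability definition is more than a 3-month look-back. The Wood's-light criterion concerns the lesion margin, where spread would occur. This makes spread less likely, but it is assessed at entry and does not exclude extension between D0 and M4.

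**Cost of the alternative.** Net area needs no alignment of sheets, whereas repigmented area inside a fixed outline does. Misalignment inflates that measure in one direction, more for small lesions, and cancels between sides only if it is similar on both. The natural marks are planned for finding lesions, and nothing assures that every lesion has enough of them for registration. This stands as a reason not to replace the net change.

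**Conclusion.** The point holds in a limited form. The objective names percentage of repigmentation. The only efficacy quantity is change in a lesion surface whose definition leaves open the inner areas and the reference outline. The product-minus-placebo contrast therefore cannot separate more repigmentation from less spread, and spread on one side can mask repigmentation there.

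On the assumed values, spread differing by 15 points of D0 area between sides produces a 15-point contrast with no repigmentation difference, and a 20-point excess of spread on the product side hides a 20-point benefit. These figures show the mechanism only. The documents give no spread rate, the entry criteria work against spread, and with no spread and inner areas subtracted the planned measure equals minus the repigmentation percentage. The actual bias could be negligible, and the documents cannot settle it.

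This is a cheap improvement. The documents do not show that the primary result is wrong or that the primary variable must be replaced.

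**What to change.** 1. In sections 2.2.1 and 1.4.1, state that lesion surface is the depigmented area with inner repigmented areas subtracted. Keep its change from D0 as the main surface measure.
2. Align each visit's tracing on the D0 tracing by the natural marks, with the standardized photographs of section 2.1 as support. Report two further quantities, per side and as product minus placebo: (a) area repigmented inside the D0 outline divided by D0 area, and (b) newly depigmented area outside the D0 outline divided by D0 area.
3. State in section 1.4 that a favourable ΔΔ% is interpreted as repigmentation only if (a) supports it.

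The cost is extra image-analysis time on tracings the sponsor already measures, and revised wording in three sections. No new visit, procedure or assessor is needed. The downside is that misalignment inflates both (a) and (b), more so for small lesions, so they should stand beside the net change and not replace it.

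### The primary objective and the expected result for lesion surface rest on change from D0 and are not tied to the product-minus-placebo difference the plan already defines

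*Combined protocol and SAP*

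**What the plan says.** The synopsis describes the design as "Comparative study, versus placebo in intra-individual". Its primary objective is to "Evaluate the percentage of repigmentation observed one month after the end of three months of treatment measured on an objective layer by image analysis". No comparator, side or size is given.

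In section 1.4, the efficacy row of the data table has lesion surface in cm² as its parameter. Its contrasts, statistical-analysis entry and expected result read "M4/D0 M3/D0 M2/D0 M1/D0 | / | Decrease". All four contrasts are against D0, the statistical-analysis column is not ticked, and the expected result is a bare direction. No other expected result for lesion surface appears in the documents.

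Section 1.4.1 defines raw and percentage changes on each side and then their difference, "\Delta\Delta = \Delta Pdt - \Delta Pla", with ΔΔ% as the percentage counterpart. These apply at every measurement time after D0, so M4 is covered. Section 1.4.2 limits the analysis to description. Section 1.4 plans 95% confidence intervals among the descriptive statistics.

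Section 1.2.2 gives Groups A and B "excimer lamp on target lesions on the two sides". Section 1.3 agrees: "Patients of both groups A and B come to the hospital where the lesions will be exposed with a Quantel 308 excimer lamp". Group C has no lamp. In the randomization list (Appendix 5.1) its line reads "Groupe C: 2 applications/ jour (matin et soir", without the lamp that is added on the lines for A and B.

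**The concern.** The placebo side is there to show what would have happened to the lesions without the product. The stated objective and the stated expectation do not use it. A change from D0 on the product side in Groups A and B combines product, lamp and natural course. In Group C it combines product and natural course.

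The protocol itself treats phototherapy as able to affect the lesions. Section 1.1.1 excludes patients who had it within the 4 weeks before randomization, and section 2.3 schedules it twice a week under the recommendations of a dermatology society.

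What is at stake is the reading of the main result. As written, a report could give the fall from D0 on the product side as the answer to the primary objective and as agreement with expectation, and leave ΔΔ% as a secondary table. Both presentations would follow the plan, yet only the second says anything about the product.

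**Working it through.** **1. How many patients are affected.** The synopsis gives a minimum of 12 in groups of 4, that is 3 × 4 = 12. Counting Appendix 5.1: A is IDs 1, 4, 5, 8; B is IDs 2, 6, 7, 12; C is IDs 3, 9, 10, 11. The list reproduces the plan's figure. Lamp on both sides: 4 + 4 = 8 of 12.

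**2. What the formulas in 1.4.1 give.** Δ% is the percentage change in surface from D0 (a decrease is negative), and ΔΔ% = Δ%Pdt − Δ%Pla.

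- Inert product, lamp reducing both sides equally by 10% to 50% (assumed): Δ%Pdt = Δ%Pla = −10 to −50, so ΔΔ% = 0. The product side shows the expected decrease.
- Product side −10%, placebo side −30%: ΔΔ% = −10 − (−30) = +20 points. The product side did worse than placebo and still shows the expected decrease. This needs no knowledge of the lamp effect.

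**3. How often an inert product would show a mean decrease.** Let m be the mean lamp effect and s the SD of the percentage change on one side. Under a normal approximation, P(mean change < 0) = Φ(−m / (s/√n)). The documents give neither m nor s, so both are assumed.

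| m | n = 4 (one lamp group), s = 20 / 30 / 40 | n = 8 (A and B), s = 20 / 30 / 40 |
|---|---|---|
| 0 | 0.50 / 0.50 / 0.50 | 0.50 / 0.50 / 0.50 |
| −10% | 0.84 / 0.75 / 0.69 | 0.92 / 0.83 / 0.76 |
| −20% | 0.98 / 0.91 / 0.84 | 0.998 / 0.97 / 0.92 |
| −30% | 0.999 / 0.98 / 0.93 | 1.00 / 0.998 / 0.98 |

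Example: m = −10, s = 30, n = 8 gives Φ(10 / (30/2.828)) = Φ(0.943) = 0.83. In Group C, with no lamp and no drift, the probability is 0.50; any spontaneous repigmentation raises it.

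**4. What the product-minus-placebo difference gives.** If the lamp acts equally on both sides, an inert product has expected ΔΔ% of 0 for every m above. Its observed mean is below 0 with probability 0.50 if the difference is symmetric. Read separately in three independent groups, at least one would be below 0 with probability 1 − 0.5³ = 0.875. A negative point estimate alone is therefore weak evidence, and the interval is needed.

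**5. Precision.** The half-width of the 95% CI for mean ΔΔ%, in units of the SD of the within-patient difference, is t(0.975, n−1)/√n. This is 1.59 at n = 4, 0.84 at n = 8 and 0.64 at n = 12.

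**The case against.** The strongest reply is that the column is headed as an expected result and nothing in the documents makes it a decision rule. The statistical-analysis column is not ticked, section 1.4.2 allows description only, and the acceptability row likewise gives a bare direction against baseline. This stands. A reader might infer that the trial has a success criterion which an inert product would meet. The documents do not support that: they set no success criterion, and without a stated lamp effect the most that can be said is that an inert product could show the expected result.

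A second reply is that the placebo contrast is already planned. Section 1.4.1 defines ΔΔ and ΔΔ%, the sides are randomized, and a lamp effect common to both sides cancels. This also stands, and it rules out the reading that the analysis lacks a placebo comparison. What is missing is the link: nothing says that ΔΔ% answers the primary objective.

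A third reply is that Group C has no lamp and that section 1.1.1 requires stable lesions. The lamp argument indeed does not reach those 4 patients. Stability at entry does not exclude repigmentation over four months, though the documents give no rate for it.

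These replies limit the point but do not remove it. In a descriptive study the written objective and expectation are the only prespecified guide to what counts as the main efficacy result, and here both omit the comparator.

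**Conclusion.** The point holds as a mismatch between design and stated objective. The study is declared comparative against placebo within the patient, but its primary objective and its only expected result for lesion surface concern change from D0 and are not linked to ΔΔ%. In 8 of 12 patients a fall from D0 on the product side cannot separate product from lamp; in the other 4 it cannot separate product from natural course.

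That conclusion rests on the documents alone. The probabilities of 0.69 to 1.00 for an inert product rest on assumed lamp effects of −10% to −30% and assumed SDs of 20% to 40%. With no lamp effect and no drift the figure is 0.50.

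The point should be settled before results are unblinded because it changes what may be concluded about the product. It is not of the gravest kind: the right quantity is already defined and will be calculated, and no data collection or randomization is affected.

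**What to change.** - Synopsis, primary objective: reword as *the within-patient product-minus-placebo difference in percentage change of lesion surface from D0 (ΔΔ%) at M4*.
- Section 1.4, efficacy row: replace the expected result with *greater decrease on the product side than on the placebo side (ΔΔ% below 0)*, M4 being primary and M1 to M3 secondary.
- Report ΔΔ% by group with the 95% CI that section 1.4 already plans. In A and B it describes the product added to the lamp, in C the product alone. The n = 8 figure applies only if A and B are pooled despite their different application frequencies.
- Add a sentence that neither a decrease from D0 on one side nor a negative point estimate of ΔΔ% alone is evidence of product efficacy.

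The cost is wording only, since the measurements and formulas exist. The price is a harder benchmark with wide intervals: about ±1.59 SD of the within-patient difference in a group of 4, and ±0.84 SD for 8 patients. Conclusions therefore remain exploratory.
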